**Table 5 Guidelines for Management of Patients Who Experience Specific Adverse Events (Cobimetinib and Atezolizumab) (cont.)**

Event	Action to Be Taken
Hemorrhage	
Grade 3 hemorrhage	
 
• Interrupt cobimetinib treatment. There are no data on the effectiveness of cobimetinib dose modification for hemorrhage events. Clinical judgment should be applied when considering restarting cobimetinib treatment.
 
• Continue atezolizumab treatment.
 

Grade 4 hemorrhage or any grade cerebral hemorrhage	
 
• Interrupt cobimetinib treatment. Permanently discontinue cobimetinib for hemorrhage events attributed to cobimetinib.
 
• Continue atezolizumab treatment.
 

Grade 3 or 4 or intolerable Grade 2 treatment-related toxicities not described above and in Table 4 (dose modifications for cobimetinib)	
 
• Withhold all study treatment.
 
• If event resolves to Grade 1 or better within 12 weeks, resume atezolizumab at fixed dose. If not, permanently discontinue atezolizumab. a, b, c
 
• If event resolves to Grade 1 or better within 28 days, resume cobimetinib with dose reduced by one level. If not, permanently discontinue cobimetinib.
 

a If corticosteroids have been initiated, they must be tapered over  $\geq 1$  month to  $\leq 10$  mg/day oral prednisone or equivalent before atezolizumab can be resumed.

b Atezolizumab may be withheld for a period of time beyond 12 weeks to allow for corticosteroids to be reduced to  $\leq 10$  mg/day oral prednisone or equivalent. The acceptable length of the extended period of time must be agreed upon by the investigator and the Medical Monitor.

c Resumption of atezolizumab may be considered in patients who are deriving benefit and have fully recovered from the immune-related event. Patients can be rechallenged with atezolizumab only after approval has been documented by both the investigator (or an appropriate delegate) and the Medical Monitor.

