**Table 4 Recommended Cobimetinib Dose Modifications**

Grade (NCI CTCAE v4.0)	Recommended Cobimetinib Dose
Grade 1 or Grade 2 (tolerable)	No dose reduction. Maintain cobimetinib at the same dose of 60 mg QD (3 tablets).
Grade 2 (intolerable) or Grade 3 or 4 (any)	
First appearance	Interrupt treatment until Grade $\leq$ 1, restart treatment at 40 mg QD (2 tablets).
Second appearance	Interrupt treatment until Grade $\leq$ 1, restart treatment at 20 mg QD (1 tablet).
Third appearance	Consider permanent discontinuation.

NCI CTCAE v4.0=National Cancer Institute Common Terminology Criteria for Adverse Events, Version 4.0; QD=once a day.

*Note: Cobimetinib dose re-escalation is permitted on a case-by-case basis after discussion with the Medical Monitor or  designee.*

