#### 5.1.3.4 **Guidelines for Management of Patients Who Experience Adverse Events**

Toxicities associated or possibly associated with cobimetinib plus atezolizumab treatment should be managed according to standard medical practice.

Refer to [Table 5](#) for management of cobimetinib- and atezolizumab-specific toxicities, including gastrointestinal toxicity, hepatotoxicity, dermatologic toxicity, pulmonary toxicity, potential eye toxicity, LVEF reduction, rhabdomyolysis and elevated CPK, hemorrhage, and systemic immune activation. Refer to [Appendix 8](#) for detailed management guidelines for atezolizumab-specific adverse events.

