- c Resumption of atezolizumab may be considered in patients who are deriving benefit and have fully recovered from the immune-related event. Patients can be rechallenged with atezolizumab only after approval has been documented by both the investigator (or an appropriate delegate) and the Medical Monitor.

**Table 5 Guidelines for Management of Patients Who Experience Specific Adverse Events (Cobimetinib and Atezolizumab) (cont.)**

Event	Action to Be Taken
Gastrointestinal toxicity (cont.)	
Colitis, Grade 2	
 
• Withhold atezolizumab and cobimetinib.
 
• Initiate supportive care and monitor patient closely.
 
• Discontinue medications that may exacerbate colitis (e.g., NSAIDs).
 
• Refer patient to GI specialist for evaluation and confirmatory biopsy.
 
• For recurrent events or events that persist > 5 days, initiate treatment with 1–2 mg/kg/day oral prednisone or equivalent.
 
• If event resolves to Grade 1 or better within 12 weeks, resume atezolizumab at fixed dose. If not, permanently discontinue atezolizumab and cobimetinib. a, b, c
 
• If event resolves to Grade 1 or better within 28 days, resume cobimetinib with dose reduced by one level. If not, permanently discontinue cobimetinib.
 

Colitis, Grade 3	
 
• Withhold atezolizumab and cobimetinib.
 
• Initiate supportive care and monitor patient closely.
 
• Discontinue medications that may exacerbate colitis (e.g., NSAIDs).
 
• Refer patient to GI specialist for evaluation and confirmatory biopsy.
 
• Initiate treatment with 1–2 mg/kg/day IV methylprednisolone or equivalent and convert to 1–2 mg/kg/day oral prednisone or equivalent upon improvement.
 
• If event resolves to Grade 1 or better within 12 weeks, resume atezolizumab at fixed dose. If not, permanently discontinue atezolizumab and cobimetinib. a, b, c
 
• If event resolves to Grade 1 or better within 28 days, resume cobimetinib with dose reduced by one level. If not, permanently discontinue cobimetinib.
 

GI = gastrointestinal; NSAID = non-steroidal anti-inflammatory drug.

- a If corticosteroids have been initiated, they must be tapered over  $\geq 1$  month to  $\leq 10$  mg/day oral prednisone or equivalent before atezolizumab can be resumed.

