Dermatologic event, Grade 1 or 2	
 
• Continue atezolizumab and cobimetinib.
 
• Initiate supportive care (e.g., antihistamines, topical corticosteroids). If event does not improve, consider treatment with higher-potency topical corticosteroids.
 
• For Grade 2 rash, consider referral to dermatologist.
 
 
Acneiform rash:
 
 
• Consider topical corticosteroids (e.g., hydrocortisone 2.5%, alclometasone) and oral antibiotics (minocycline, doxycycline, or antibiotics covering skin flora) as clinically indicated.
 

Dermatologic event, Grade 3	
 
• Withhold atezolizumab and cobimetinib.
 
• Refer patient to dermatologist. A biopsy should be performed if appropriate.
 
• Consider initiating treatment with 10 mg/day oral prednisone or equivalent, increasing dose to 1–2 mg/kg/day if event does not improve within 48–72 hours.
 
• If event resolves to Grade 2 or better within 12 weeks, resume atezolizumab at fixed dose. If not, permanently discontinue atezolizumab and cobimetinib.a, b
 
• Permanently discontinue atezolizumab and cobimetinib and contact Medical Monitor if event does not resolve to Grade 1 or better within 12 weeks.a, b, c
 
• If event resolves to Grade 2 or better within 28 days, resume cobimetinib with dose reduced by one level. If not, permanently discontinue cobimetinib.
 
 
Acneiform rash:
 
 
• Consider continuation of topical corticosteroids (e.g., 2.5% alclometasone) and oral antibiotics (e.g., minocycline, doxycycline, or antibiotics covering skin flora) when restarting cobimetinib.
 

Dermatologic event, Grade 4	
 
• Permanently discontinue atezolizumab and cobimetinib, and contact Medical Monitor.c
 

a If corticosteroids have been initiated, they must be tapered over  $\geq 1$  month to  $\leq 10$  mg/day oral prednisone or equivalent before atezolizumab can be resumed.

b Atezolizumab may be withheld for a period of time beyond 12 weeks to allow for corticosteroids to be reduced to  $\leq 10$  mg/day oral prednisone or equivalent. The acceptable length of the extended period of time must be agreed upon by the investigator and the Medical Monitor.

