c Resumption of atezolizumab may be considered in patients who are deriving benefit and have fully recovered from the immune-related event. Patients can be rechallenged with atezolizumab only after approval has been documented by both the investigator (or an appropriate delegate) and the Medical Monitor.

**Table 5 Guidelines for Management of Patients Who Experience Specific Adverse Events (Cobimetinib and Atezolizumab) (cont.)**

Event	Action to Be Taken
Pulmonary events	
General guidance	Mild-to-moderate events of pneumonitis have been reported with atezolizumab and cobimetinib. All pulmonary events should be thoroughly evaluated for other commonly reported etiologies such as pneumonia/infection, lymphangitic carcinomatosis, pulmonary embolism, heart failure, chronic obstructive pulmonary disease, or pulmonary hypertension. For events concerning for pneumonitis, consider comprehensive infectious evaluation including viral etiologies.
Pneumonitis, Grade 1 (asymptomatic)	
 
• Continue atezolizumab and cobimetinib.
 
• Re-evaluate on serial imaging.
 
• Consider patient referral to pulmonary specialist.
 

Pneumonitis, Grade 2	
 
• Withhold atezolizumab and cobimetinib.
 
• Refer patient to pulmonary and infectious disease specialists and consider bronchoscopy or BAL.
 
• If bronchoscopy is consistent with immune-related etiology, initiate treatment with 1–2 mg/kg/day oral prednisone or equivalent.
 
• Resume atezolizumab and cobimetinib if event resolves to Grade 1 or better within 12 weeks. a, b
 
• Permanently discontinue atezolizumab and cobimetinib and contact Medical Monitor if event does not resolve to Grade 1 or better within 12 weeks. a, b, c
 
• For recurrent events, treat as a Grade 3 or 4 event.
 

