## **Appendix 8**

### **Risks Associated with Atezolizumab and Guidelines for Management of Adverse Events Associated with Atezolizumab (cont.)**

dermatologist should evaluate persistent and/or severe rash or pruritus. A biopsy should be considered unless contraindicated.

Management guidelines for dermatologic events are provided in Section [5.1.3.4](#).

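### Table 5 gives opposite instructions for a Grade 3 skin event that is at Grade 2 at week 12, and its ALT/AST Grade 2 and 3 rows overlap, leave gaps or are empty depending on the patient's baseline

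*Combined protocol and SAP*

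**What the plan says.** **Skin.** The Dermatologic event, Grade 3 row of Table 5 contains three time-limited bullets:

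- atezolizumab, 12 weeks: "If event resolves to Grade 2 or better within 12 weeks, resume atezolizumab at fixed dose. If not, permanently discontinue atezolizumab and cobimetinib"
- both drugs, 12 weeks: "Permanently discontinue atezolizumab and cobimetinib and contact Medical Monitor if event does not resolve to Grade 1 or better within 12 weeks"
- cobimetinib, 28 days: "If event resolves to Grade 2 or better within 28 days, resume cobimetinib with dose reduced by one level"; otherwise cobimetinib stops for good.

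Elsewhere in Table 5 the 12-week rule has a single threshold. The colitis Grade 2 and 3 rows say "If event resolves to Grade 1 or better within 12 weeks, resume atezolizumab at fixed dose. If not, permanently discontinue atezolizumab and cobimetinib", and pneumonitis Grade 2 says "Resume atezolizumab and cobimetinib if event resolves to Grade 1 or better within 12 weeks". Section 5.1.3.4 refers the reader to Appendix 8 "for detailed management guidelines for atezolizumab-specific adverse events". The skin text of Appendix 8 refers back: "Management guidelines for dermatologic events are provided in Section" 5.1.3.4. Appendix 8 does the same for hepatic events.

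**Liver.** With total bilirubin below 2×ULN, the Grade 1 row runs from above ULN to 3×ULN. The Grade 2 row runs from above 3 times baseline to below 5×ULN, and the Grade 3 row from above 5 times baseline to below 10×ULN. A further row covers values above 10×ULN. Section 4.1.1.1 admits patients with ALT and AST up to 2.5×ULN, or 5×ULN with documented liver metastases.

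**The concern.** The two skin bullets share one clock but use different thresholds, and their actions are opposite. Whether a patient at Grade 2 at week 12 continues or permanently loses both drugs depends on which bullet the site follows.

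The liver rows combine two scales, so the same ALT value can match several rows or none. Where rows overlap, all start from continuing treatment, but they differ in two ways:

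- **Liver tests:** every 4 weeks under Grade 1, at least weekly under Grades 2 and 3.
- **Suspected immune-related event:** no instruction under Grade 1, consider withholding atezolizumab after 5 days under Grade 2, withhold it under Grade 3.

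Where no row matches, nothing in Table 5 triggers weekly tests, and Appendix 1 schedules chemistry only on Day 1 of each 28-day cycle. Similar patients could be managed differently across sites. The Section 6.5 counts of adverse events leading to discontinuation or interruption would then partly reflect which reading each site chose.

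**Working it through.** No stated figure needs reproducing; the check applies the written rules to possible values.

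**Skin row at week 12**

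| Grade at week 12 | Resume bullet (needs ≤2) | Stop bullet (applies if >1) | Result |
|---|---|---|---|
| 0–1 | met | not met | resume |
| 2 | met | met | both |
| 3–4 | not met | met | stop |

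A staged reading is possible: resume on reaching Grade 2, then stop if Grade 1 is not reached by week 12. The text does not state it. It would make the second sentence of the first bullet redundant, because an event above Grade 2 is already stopped by the next bullet. An event first reaching Grade 2 at week 12 would be resumed and stopped at once. The row's footnotes cover steroid taper, longer withholding to allow the taper, and rechallenge after full recovery; none ranks the bullets.

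Eight Table 5 rows carry a 12-week rule: diarrhea (intolerable Grade 2 or Grade 3), colitis Grade 2, colitis Grade 3, dermatologic Grade 3, ALT/AST Grade 2, ALT/AST Grade 3, pneumonitis Grade 2 and the catch-all. Seven use Grade 1 alone. Only the skin row has two thresholds.

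**Liver rows** (bilirubin below 2×ULN)

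Let b = baseline/ULN and v = value/ULN.

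- Grade 1: 1 < v ≤ 3
- Grade 2: 3b < v < 5, empty when 3b ≥ 5, that is b ≥ 5/3 = 1.67
- Grade 3: 5b < v < 10, empty when 5b ≥ 10, that is b ≥ 2
- Top row: v > 10

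For b < 1, Grades 2 and 3 overlap on 5b < v < 5, and Grades 1 and 2 overlap on 3b < v ≤ 3. For 1 < b < 1.67 there are gaps at 3 < v ≤ 3b and 5 ≤ v ≤ 5b; at b = 1.5 these run from 3 to 4.5 and from 5 to 7.5. For b ≥ 2 no row applies from above 3 up to and including 10.

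| b | v | v/b | Grade 2 range | Grade 3 range | Rows matched |
|---|---|---|---|---|---|
| 0.5 | 2.8 | 5.6 | 1.5–5 | 2.5–10 | Grades 1, 2 and 3 |
| 1.2 | 5.5 | 4.6 | 3.6–5 | 6–10 | none |
| 2 | 8 | 4 | empty | empty | none |
| 2.5 | 9 | 3.6 | empty | empty | none |

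The last three are clear rises at baselines open to patients without liver metastases.

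**The case against.** The strongest reply is that these are guidelines. Section 5.1.3.4 asks for management by standard medical practice, and Section 4.5 allows dosing only if clinical and laboratory assessments are acceptable. The second skin bullet requires contact with the Medical Monitor, and the liver rows carry grade labels that a site could fall back on. This stands as mitigation. It limits the harm but does not tell a site which skin bullet governs. In the liver gaps, the Grade 3 label points to continuing all treatment. The catch-all row would withhold all treatment, but it covers toxicities not already described, and ALT/AST elevations arguably are described.

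Numbers are probably small. As a rough illustration for skin, the 150-patient combination study in Section 1.2.6.2 lists no rash term among Grade ≥3 events at 5% or more. Section 5.1.1.3.1 gives about 16% Grade ≥3 rash, with about 90% of those events resolving, for cobimetinib plus vemurafenib. Assuming 10% unresolved among 250 patients gives 250 × 0.05 × 0.10 = 1.25 to 250 × 0.16 × 0.10 = 4 patients, and those at exactly Grade 2 are a subset. This is not a bound: the 5% is per term, resolution is not dated to week 12, and the partner drug differs.

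Three stronger readings are tempting but unsupported:

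- **Restarting cobimetinib at Grade 2 is an error because Table 4 waits for Grade 1.** Table 5 departs from Table 4 elsewhere: CPK elevation restarts at Grade 3 or lower, and the ALT/AST Grade 3 row continues all treatment. The difference is not itself a fault.
- **Grade 2 is the wrong skin threshold.** The adjacent Grade 1 or 2 row continues both drugs, and two of the three Grade 3 bullets use Grade 2, so either threshold is defensible.
- **Multiples of baseline are a mistake.** Section 5.3.5.7 also uses 3 times baseline, so the anchoring looks deliberate. The fault lies in combining it with ULN upper bounds.

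**Conclusion.** Both faults hold on the text. The skin row gives opposite instructions at Grade 2 at week 12, and nothing else in the documents settles them. The liver rows overlap below a baseline of 1×ULN, leave gaps above it, and are both empty from 2×ULN. An eligible patient can therefore rise from 2 to 8×ULN, with bilirubin below 2×ULN, without matching any row until the value exceeds 10×ULN. Values of exactly 5 and 10×ULN also match no row at a baseline of 1×ULN, but that is trivial.

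How many patients are affected cannot be determined: the documents give no baseline ALT/AST distribution and no week-12 grade for unresolved rash. A reader might infer that the efficacy result is compromised. The documents do not support that. The ORR definition, its analysis and the sample size do not depend on these rows. The consequence is confined to patient management and the Section 6.5 discontinuation and interruption summaries. That is enough to justify correction, given the low cost.

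**What to change.** **Skin Grade 3 row.** Keep one week-12 threshold for atezolizumab and delete the conflicting bullet. Grade 2 or better fits the adjacent row; Grade 1 or better fits the other seven 12-week rows. Leave the 28-day cobimetinib bullet alone unless the sponsor chooses to change it. Moving it to Grade 1 would permanently end cobimetinib for a patient at Grade 2 on day 28, which is a treatment change.

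**Liver rows.**

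- Grade 2: above the lower of 3×baseline and 3×ULN, up to and including 5×ULN.
- Grade 3: above the lower of 5×baseline and 5×ULN, up to and including 10×ULN.
- The highest matching row applies.
- If baseline exceeds ULN, also require worsening from the baseline grade and a stated minimum rise (for example 1.5-fold, sponsor to choose). Otherwise standard monitoring continues.
- Define resolution as Grade 1 or return to baseline, because Grade 1 lies below baseline for a patient entering above 3×ULN.

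Check: (b, v) = (0.5, 2.8), (1.2, 5.5), (2, 8) and (2.5, 9) all fall in Grade 3. A stable patient at 4×ULN triggers nothing. A move from 4.9 to 5.1×ULN is a 1.04-fold rise and triggers nothing; 4 to 9.5×ULN is 2.4-fold and falls in Grade 3.

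Putting every bound on ULN alone would be simpler but worse. The (0.5, 2.8) patient would drop from weekly to 4-weekly tests, and the 4.9 to 5.1×ULN patient would enter the Grade 3 row.

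The cost is amendment or clarification-letter wording, plus weekly liver tests for patients who now match no row. Sample size, tumor assessments and analyses do not change.

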### **4.3.2 Dosage, Administration, and Compliance**

#### **4.3.2.1 Cobimetinib**

Patients will receive cobimetinib 60 mg (3 tablets of 20 mg each) orally QD on Days 1–21 of each 28-day cycle in all cohorts. This 4-week period is considered a treatment cycle.

Cobimetinib should be taken at the same time every day. It can be taken with or without food. If a dose of cobimetinib is missed or if vomiting occurs when the dose is taken, patients may resume dosing with the next scheduled dose.

Guidelines for dosage modification and treatment interruption or discontinuation of cobimetinib are provided in Section [5.1.3.1](#).

Any dose modification should be noted on the Study Drug Administration electronic Case Report Form (eCRF). Cases of overdose, medication error, drug abuse, or drug misuse, along with any associated adverse events, should be reported as described in Section [5.4.4](#).

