c Resumption of atezolizumab may be considered in patients who are deriving benefit and have fully recovered from the immune-related event. Patients can be rechallenged with atezolizumab only after approval has been documented by both the investigator (or an appropriate delegate) and the Medical Monitor.

**Table 5 Guidelines for Management of Patients Who Experience Specific Adverse Events (Cobimetinib and Atezolizumab) (cont.)**

Event	Action to Be take
Elevations in ALT, AST, and/or bilirubin	
AST/ALT >ULN to $\leq 3 \times$ ULN with total bilirubin < $2 \times$ ULN (Grade 1)	
 
• Continue atezolizumab and cobimetinib.
 
• Continue with the standard monitoring plan (i.e., LFTs Q4W before dosing).
 

AST/ALT > $3 \times$ baseline values to < $5 \times$ ULN with total bilirubin < $2 \times$ ULN (Grade 2)	
 
• Continue all study treatment.
 
• Monitor LFTs at least weekly.
 
• Consider referral to a hepatologist and liver biopsy.
 
• For suspected immune-related events of > 5 days duration               
 
– Consider withholding atezolizumab. a
 
– Consider administering 1–2 mg/kg/day oral prednisone or equivalent followed by <math>\geq 1</math> month taper.
 
– Restart atezolizumab if event resolves to Grade 1 or better within 12 weeks. b, c
 
– Permanently discontinue atezolizumab and cobimetinib if event does not resolve to Grade 1 or better within 12 weeks. a, b, c
 
 
 

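### Table 5's Grade 3 dermatologic row gives two incompatible week-12 rules: a rash at Grade 2 qualifies both to resume atezolizumab and to stop both drugs permanently

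*Combined protocol and SAP*

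**What the plan says.** In Table 5 (Section 5.1.3.4), the row for a Grade 3 dermatologic event withholds both drugs, refers the patient to dermatology and suggests a steroid. It then gives three recovery rules, called A, B and C here.

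- **A, atezolizumab:** "If event resolves to Grade 2 or better within 12 weeks, resume atezolizumab at fixed dose". If that is not met, both drugs stop permanently. Footnotes a and b are attached.
- **B, both drugs:** "Permanently discontinue atezolizumab and cobimetinib and contact Medical Monitor if event does not resolve to Grade 1 or better within 12 weeks". Footnotes a, b and c are attached.
- **C, cobimetinib:** "If event resolves to Grade 2 or better within 28 days, resume cobimetinib with dose reduced by one level". If that is not met, cobimetinib stops permanently.

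Footnote a requires a steroid taper before atezolizumab is resumed. Footnote b lets the atezolizumab hold run past 12 weeks for that taper. Footnote c says "Resumption of atezolizumab may be considered in patients who are deriving benefit and have fully recovered from the immune-related event", with documented approval from the investigator and the Medical Monitor. Appendix 8, under dermatologic events, sets no rule of its own: "Management guidelines for dermatologic events are provided in Section" 5.1.3.4, which leads back to Table 5.

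**The concern.** Rules A and B set different recovery grades for the same event, the same 12-week window and the same drug. An investigator with a patient whose rash has settled at Grade 2 at week 12 can cite the row for resuming atezolizumab and equally for ending all study treatment. Two sites could treat identical patients in opposite ways, and each could claim to have followed the protocol. At stake is either re-exposure of a patient the sponsor meant to take off treatment, or loss of treatment for a patient the sponsor meant to keep on it.

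**Working it through.** The plan states no figure on this point. The check sets the rules side by side.

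**Step 1. Apply A and B to each grade at week 12.**

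| Grade at week 12 | Rule A | Rule B | Consistent? |
|---|---|---|---|
| 0 | resume atezolizumab | no stop | yes |
| 1 | resume atezolizumab | no stop | yes |
| 2 | resume atezolizumab | stop both permanently | **no** |
| 3 or higher | stop both permanently | stop both permanently | yes |

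The conflict sits at Grade 2 only.

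**Step 2. Can A and B be read in sequence?** Suppose A opens a restart at Grade 2 and B sets a Grade 1 deadline at week 12. For a rash that reaches Grade 2 early, both could then be obeyed at different times. But A carries its own permanent-stop clause, set at failure to reach Grade 2. The row would still hold two permanent-stop thresholds for one window, and a rash that first reaches Grade 2 at week 12 leaves no interval in which to apply them in turn.

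**Step 3. Cobimetinib.** Assume that the windows in B and C start on the same day, since the row does not name the starting day.

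- Latest restart under C: day 28, at Grade 2.
- Permanent stop under B, if B prevails: 12 × 7 = day 84.
- Minimum time from restart to stop: 84 − 28 = 56 days, and longer if the restart was earlier.

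So a rash good enough to restart cobimetinib at day 28 could, unchanged, end cobimetinib at day 84.

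**Step 4. Does other text resolve it?**

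- Footnotes a and b deal with steroid taper and the length of the hold. They do not touch the recovery grade.
- Footnote c concerns atezolizumab only and requires full recovery, which a rash still at Grade 2 has not reached.
- Appendix 8 sends the reader back to the same table.

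**Step 5. What do neighboring rules use?**

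| Rule | Recovery grade |
|---|---|
| Table 4, cobimetinib restart | Grade 1 or better |
| Diarrhea, Grade 2 (intolerable) or 3: week 12 and day 28 | Grade 1 or better |
| Colitis, Grade 2 and Grade 3: week 12 and day 28 | Grade 1 or better |
| Pneumonitis, Grade 2: week 12, both drugs | Grade 1 or better, for resuming and stopping alike |
| Dermatologic, Grade 3 | Grade 2 in A and C, Grade 1 in B |

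Only the dermatologic row mixes grades.

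**The case against.** The defense has three good points. First, the conflict is narrow: one grade at one time. Second, a rash that improves early can mostly be handled in sequence, as Step 2 allows. Third, there are safeguards: rule B requires contact with the Medical Monitor, the bullets are adjacent, and Grade 3 or higher rash is an adverse event of special interest that must reach the Sponsor within 24 hours (Section 5.2.3). Opposite treatment at two sites is therefore possible, not inevitable, and the 56 days arise only if B is taken to prevail. All of that stands. It does not remove the contradiction: the contact instruction sits in B, so an investigator applying A is not told to call, and event reporting does not say which rule applies.

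A reader might go further and infer that Table 4 also clashes with much of Table 5. Its second category is "Grade 2 (intolerable) or Grade 3 or 4 (any"), with interruption to Grade 1 or better and restart at 40 mg on first appearance. At least 10 explicitly graded Table 5 rows prescribe something else for cobimetinib: 6 stop it permanently, 2 continue it and 2 restart it at a higher grade. Section 4.3.2.1 also points to Table 4 alone: "Guidelines for dosage modification and treatment interruption or discontinuation of cobimetinib are provided in Section" 5.1.3.1.

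The documents do not support calling these 10 contradictions. The word in parentheses contrasts with tolerable and intolerable in the adjacent labels, so it most naturally means Grade 3 or 4 regardless of tolerability. Table 4 is titled as recommended modifications and reads as a general default. Section 5.1.3.4 sends readers to Table 5 "for management of cobimetinib- and atezolizumab-specific toxicities, including gastrointestinal toxicity, hepatotoxicity, dermatologic toxicity, pulmonary toxicity" and further named toxicities. Section 4.3.2.2 and the hemorrhage risk section route to Section 5.1.3.4 as well, and the retinopathy, left ventricular and CPK sections route to Section 5.1.3 as a whole. Event-specific departures from a default are expected. What remains is a cross-reference in Section 4.3.2.1 that is too narrow.

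**Conclusion.** Wrong as written, as a safety dosing rule. One row of Table 5 contradicts itself for a rash at Grade 2 at week 12, and no footnote, appendix or order of precedence between tables can settle a conflict inside a single row. It should be corrected.

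The number of patients affected cannot be computed, because the documents give no rate for a Grade 3 rash that stands at Grade 2 at week 12. Related figures suggest few. In Study GP28363, rash of any grade occurred in 46.0% of 150 patients, but rash is not among the Grade 3 or higher events listed at 5% or more. With cobimetinib plus vemurafenib, Grade 3 or higher rash was about 16%, similar in both arms, and about 90% of these events resolved (Section 5.1.1.3.1).

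It would be a mistake to infer damage to the efficacy results. ORR, the time-to-event endpoints and the sample size are defined independently of this rule. The effect is on patient safety and on consistent dosing, and so on the descriptive exposure and discontinuation summaries in Section 6.5, which record whichever rule a site followed.

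**What to change.** **Dermatologic row, Grade 3.** Use one recovery grade for resuming atezolizumab at week 12, for the week-12 permanent stop and for the 28-day cobimetinib restart.

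- *Grade 1 or better* is the consistent choice, for the reasons in Step 5. Change the grade in rules A and C, and keep B. The cost is somewhat more holds or discontinuations, falling on patients whose rash settles at Grade 2.
- *Grade 2 or better* is defensible if it is what the sponsor intends, since Table 5 continues both drugs for a dermatologic event that is Grade 1 or 2 from the start. In that case delete rule B, and move its Medical Monitor contact and footnote c to rule A's stop clause.

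**Minor companion changes.** Have Section 4.3.2.1 also cite Section 5.1.3.4, and add a note to Table 4 that event-specific rows in Table 5 take precedence. Leave the parenthetical qualifier in Table 4 and the residual row of Table 5 as they are. Removing the qualifier would lose the tolerability distinction. Redrawing the residual row could make both tables cover the same unlisted toxicities under different rules, because that row withholds all study treatment and sets a 28-day cobimetinib limit, and Table 4 does neither.

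The work is a few words in one row, one table note and one cross-reference, to be made by amendment. No sample size or analysis text changes.
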